### Randomized Controlled Trial

The primary outcome for this study is the proportion of delivery clients each TBA successfully refers for postnatal care within 48 hours of delivery.

The team will conduct postnatal care observation surveys in potential study villages. We will select villages that meet the criteria outlined in Section 3.1.

At baseline, trained enumerators will interview TBAs and complete a survey over 60 minutes in a private location chosen by the TBA. The information collected will include demographic data, stated motivation for services, description of services provided, and social network of the TBAs. We will make photo recordings of these interactions (between TBAs and enumerators) for the purpose of presentation as described below.

All TBAs that participate in the study will receive the following:

- Information on the study aims (attached to submission), the need for postnatal care attendance, and verbal encouragement to refer delivery clients to postnatal care within 48 hours of childbirth
- Offer of two-weekly cumulative payouts of \$0.70 per reported delivery they take that is verified by client.
- Each TBA will be assigned an identification number (TBA ID) and randomized with 50-50 probability to the referral incentive or control arm.

TBAs randomized to the referral incentive arm will also receive an offer of two-weekly cumulative payouts of \$2.00 per successful referral of delivery clients to early postnatal care in a facility if it is verified by the client. Delivery clients are women who have given birth assisted by the TBA. Verification is described below.

Thus, the required follow-up surveys will be conducted every two-weeks, consisting of:

- Self-reported deliveries by TBAs obtained via SMS messages sent by TBAs to the study team. TBAs will be asked to send a text message after each delivery they oversee. TBAs will text the name and contact details (phone number and address) of clients delivered over the past two weeks. Two-weekly calls will also be made by the study team to the TBAs to ensure that all deliveries are reported. Data to be recorded includes TBA name as well as TBA delivery client name, phone number, and address.

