- Calls to women who TBAs report they delivered (TBA delivery clients) – these calls will ascertain delivery by TBA, date of delivery, date and location of attendance of postnatal care (if attended), referral to postnatal care by TBA, incidence of delivery and postnatal complications. In these contexts, delivery of a child and where delivery occurs is often common knowledge. The TBA is often involved in the naming ceremony that holds soon after. The study team will nevertheless recruit TBAs who are willing to share this information and allow both TBAs and their clients to opt out of the study.
- For a random subset of mothers, we will back-check the facility attendance registers to confirm postnatal care attendance. We will attach approval for access to patient information as a modification.

The anticipated duration of the intervention is September 2016 to January 31, 2017.

As part condition for the receipt of one of the study grants (Women and Public Policy Program's Cultural Bridge Fellowship), the study coordinator will blog on field research activities related to both the focus group discussions and randomized controlled trials. These blogs will contain pictures of survey respondents or focus group participants, for which informed consent will be sought.

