#### **7.4. Describe the minimum qualifications for each research role (e.g., RN, social worker) their experience in conducting research, and their knowledge of local study sites and culture**

##### A. Field Work Enumerator

#### Tasks

1. Participate fully in field work training
2. Assist field work manager and principal investigator in all activities related to the project – including data collection, pre-tests, study pilots, and participant enrollment
3. Travel to study districts and other duties as necessary

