#### Randomized Controlled Trial

Informed consent will be obtained by field enumerators. In the case of TBA delivery clients, the consent form will be delivered orally in the preferred language (English or Igbo language). A signature will be asked for, for in-person interviews in the case of TBAs. The consent discussion will last about 20 minutes. Potential participants will be given the opportunity to opt out, postpone the decision about joining, consent and postpone the survey, or consent and partake in a survey. The field enumerators will be trained to avoid coercion during the consent process. Study staff will continue to ensure participants understand what the research is about and what their participation involves. There will be numerous opportunities during recruitment and obtaining informed consent for participants to opt out of the study. Any new information which might influence a participant's decision to continue participation will be provided to participants including re-consent.

Attached:

- Randomized Controlled Trial Consent Form – TBA
- Randomized Controlled Trial Consent Form – TBA Delivery Client (verbal consent only via phone)

We will provide each participant with the contact information of a local research team member to communicate their request to have results sent to them when available.

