### **14. Participant Privacy**

#### **14.1. Describe provisions to protect participants' privacy (their desire to control access of others to themselves, e.g., the use of a private interview room) and to minimize any sense of intrusiveness that may be caused by study questions or procedures**

Group and individual interviews will be conducted in a private place, at the participant's convenience.

In the randomized controlled trial, we will ask TBAs to give us the names, addresses, and phone numbers of clients they deliver on a two-weekly basis. Follow-up calls to these clients will involve eliciting consent for inclusion in the study and ascertaining that delivery and referral by the TBA occurred. That is, we obtain information on the primary outcome of the study through follow-up surveys with TBA clients. Self-reports by TBAs given the incentives offered are likely to be unreliable.

The procedure of informed consent will be non-coercive and conducted in the language of choice for both the TBA and her clients. In these settings, it is not generally private information that a woman was pregnant, where she lives, and that she has delivered, and where she delivered. However, we will allow both the TBA and her clients to opt out of the study at any point that they consider the study procedures intrusive. The TBA and her clients will be informed of this provision. As long as drop-out of the study is non-differential across arms and is not in high proportions, this will not affect our ability to estimate effects.

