**15.3. Indicate how research team members and/or other collaborators are permitted access to information about study participants**

Field enumerators will only have access to data when during collection. Only the Harvard study team will have access to the entire study data.

The field work manager requires access to identifiable information about traditional birth attendants to implement the intervention – providing rewards for postnatal care referrals. Thus traditional birth attendants will inform the study team on a two-weekly basis of deliveries taken. Follow-up of these clients to ascertain postnatal care referrals will form the basis for determining rewards.

**15.4. If future use of data, data sharing, i.e., required of NIH-funded studies using/generating large-scale human genomic data, or future open access, i.e., free availability and unrestricted use, of data is planned or likely, indicate how data will be shared/released.**

No directly identifiable information will be made available to anyone other than the PI and Harvard faculty collaborators. Data in which names of participants will be replaced with an ID code may be shared with other collaborators as permitted in the consent form.

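### The client phone report that supplies the primary outcome also triggers a payment made in one arm only, and nothing in the plan keeps callers unaware of arm

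*Protocol*

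**What the plan says.** **Outcome and source.** Protocol 4.6 defines the endpoint: "The primary outcome for this study is the proportion of delivery clients each TBA successfully refers for postnatal care within 48 hours of delivery". Section 14.1 gives the source: "we obtain information on the primary outcome of the study through follow-up surveys with TBA clients". The mode in 4.6 is "Calls to women who TBAs report they delivered", asking for the delivery date and for the date and place of any postnatal visit.

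**Payment.** Under 4.6 and 16.2, both arms receive $0.70 per client-verified delivery. Only the incentive arm also receives $2.00 per client-verified early referral. Section 15.3 makes the link explicit: "Follow-up of these clients to ascertain postnatal care referrals will form the basis for determining rewards".

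**Staff.** Section 14.1 puts consent and outcome in one contact: "Follow-up calls to these clients will involve eliciting consent for inclusion in the study and ascertaining that delivery and referral by the TBA occurred". On trial consent, 9.1 says: "Informed consent will be obtained by field enumerators". The enumerator's tasks in 7.4 cover all project activities, "including data collection, pre-tests, study pilots, and participant enrollment". The field work manager supervises the enumerators (7.4) and implements the rewards (15.3).

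**Records and checks.** Section 4.6 holds the TBA's name alongside the client's name, phone number and address. It also provides a facility-register back-check for a random subset of mothers. The SAP contains two regression models and says nothing about how the outcome is ascertained or how the back-check is used.

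**The concern.** The only primary outcome is an interview answer, and in one arm a positive answer is worth money to a third party. If the caller knows which arm the TBA is in, small differences in conduct feed directly into the treatment coefficient: one more call-back, a further prompt, or a generous reading of the visit date.

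The 48-hour limit makes this easy. The call records dates, so a visit two calendar days after birth can fall on either side of the limit. The villages are chosen for a first routine visit at 24 to 72 hours (3.1), so visits near the limit should be common.

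The protocol accepts in 14.1 that incentives make TBAs' own reports unreliable. It does not carry that reasoning over to the client call that decides the same payment.

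**Working it through.** **1. Can the plan as written keep callers unaware of arm?** Setting the sections side by side:

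- 4.6 does not name the caller. That enumerators call clients follows from 14.1 (consent and outcome in the same call) together with 9.1 and 9.5 (enumerators take clients' consent).
- The caller has to know which TBA is concerned: she confirms delivery by that TBA (4.6) and tells the client that the TBA supplied her details (9.5). Anyone who knows that TBA's offer therefore knows the arm.
- Neither document mentions masking of callers, separate enrolment and follow-up teams, or withholding of allocation.
- De-identification (15.2) follows the intervention, too late to mask a caller.
- Leaving the incentive out of TBA consent (9.5) conceals it from TBAs, not from staff.
- The back-check (4.6) has no stated size, balance between arms or rule for discordant records.
- The other use of registers (10.1) starts when a TBA notices a disparity. For a missed referral, only incentive-arm TBAs have $2.00 at stake, so this correction could itself differ by arm.

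**2. The plan's precision.** Inputs from 5.2: difference 0.20, SD 0.37, two-sided alpha 0.05, power 90%, 1:1 allocation.

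- n per arm = 2 × (1.960 + 1.282)² × 0.37² / 0.20² = 71.9, so 72 per arm and 144 in total.
- The protocol states 160, which gives 92.8% power. 144 / 0.9 = 160 would fit a 10% loss allowance, but none is stated. The figure is conservative and is not part of this point.
- SE of the difference = 0.37 × √(4/N): 0.0585 at 160 TBAs and 0.0523 at 200.
- Smallest significant difference = 1.96 × SE: 0.115 at 160 and 0.103 at 200.

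**3. Assumed size of differential recording.** The documents give no rate. Take 2 to 5 percentage points of extra positive answers in the incentive arm.

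- Share of target: 0.02/0.20 = 10%; 0.05/0.20 = 25%.
- In clients: 5 deliveries a month for 5 months is 25 per TBA, so 25 × 0.02 = 0.5 and 25 × 0.05 = 1.25 clients per TBA over the whole trial.
- With no true effect and bias b, the chance of a significant result is Φ(b/SE − 1.96) + Φ(−b/SE − 1.96):

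| b | 160 TBAs | 200 TBAs |
|---|---|---|
| 0 | 5% | 5% |
| 0.02 | 6% | 7% |
| 0.05 | 14% | 16% |

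**4. How much misrecording is that?** Let p be the true early-attendance proportion, equal in both arms, and f the share of the remaining clients wrongly counted as early attenders in the incentive arm only. Then b = f × (1 − p), so f = b/(1 − p).

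- For p = 0.1, f runs from 0.02/0.9 = 2.2% to 0.05/0.9 = 5.6%.
- For p = 0.5, f runs from 0.02/0.5 = 4% to 0.05/0.5 = 10%.
- To reach significance on bias alone, f would have to be 13% (p = 0.1) to 23% (p = 0.5) at 160 TBAs, or 11% to 21% at 200.

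**The case against.** A reader might infer that the outcome is unblinded by design, or that arm knowledge is the default for callers. The documents do not support that.

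- TBA consent leaves out the referral incentive (9.5). As written it is the same in both arms, so enrolling a TBA reveals no allocation.
- Rewards sit with the field work manager (15.3). No section has an enumerator explain the incentive or work out a payout during follow-up. Enumerators debrief TBAs about it only after all follow-up data are in (9.5).
- Section 15.3 limits enumerators' access to data to the time of collection.
- The enumerator task list is a general job description. It shows one role covering enrolment and data collection, not that the same individuals do both.
- No enumerator's pay depends on the answers. The call asks for specific facts, and attendance can be checked against a register.

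All of this stands, and it limits the claim to what the plan leaves open. It does not close the gap. The manager who implements the rewards also directs the enumerators, no section withholds allocation from callers, and the one objective check has no stated size and no place in the analysis.

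**Conclusion.** The concern holds as an unprotected route to differential ascertainment of the only primary outcome. It is not evidence that callers know the arm or that they would behave differently if they did.

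The size is an assumption. At 2 to 5 points the bias is 10% to 25% of the target difference. With no true effect, it would raise the 5% error rate to about 6% to 14% at 160 TBAs and 7% to 16% at 200. These rates use the protocol's SD of 0.37 in a simple two-arm comparison of TBA-level proportions. Bias in this range would not reach the significance threshold by itself, but it would inflate the estimate whether or not significance changed. The change is worth making because it is cheap and cannot be made after the calls have been completed.

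**What to change.** In protocol 4.6:

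1. Give callers lists with client name, phone number, address and TBA name, but no arm or payment status. Take the delivery date from the client, not the TBA: it starts the 48-hour window, and the TBA may be paid on the result.
2. Use one script and one call-back rule in both arms.
3. Where existing staffing allows, have client calls made by someone who has not discussed the incentive or payouts with that TBA. Have the field work manager determine payouts from completed call records.
4. Draw the back-check sample with equal fractions per arm.

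In the SAP, report agreement between client report and register by arm, for attendance and, where the register shows it, for the visit date.

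The cost is some reassignment of call lists. The documents give no enumerator count, so whether item 3 can be met everywhere is unknown. Some callers may still guess the arm, which is why agreement by arm should be reported as well.

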**4.7. Does the study involve the collection of data/specimens (including the use of existing data/specimens)?**

No  Yes: If yes; indicate how, when, where and from whom specimens or data will be obtained

**4.8. Is there a data and safety monitoring plan (required for greater than minimal risk studies)?**

No  Yes: If yes; describe the plan

**4.9. Are there any anticipated circumstances under which participants will be withdrawn from the research without their consent?**

No  Yes: If yes; describe the circumstances as well any associated procedures to ensure orderly termination

TBAs, TBA delivery clients, and health workers will not be withdrawn from the study without their consent.

**5. Data/Statistical Analyses Plan**

**5.1. Briefly describe the plan for data analysis (including the statistical method if applicable)**

Qualitative Data Analysis:

If carried out in Igbo, interviews will be translated to English language. All interviews will be transcribed verbatim in Microsoft Word, following which recordings will be destroyed. Transcription will ensure that grammar, sentence structure, pauses, and unfinished sentences are preserved as much as possible. Written notes will be expanded immediately after the discussions. For both written and recorded notes, we will label discussion inputs using pseudonyms as described above – all personal identifying information will be destroyed within one month of discussions. Finally, ahead of analysis, we will read each transcript and set of notes twice to ensure immersion within the dataset. Qualitative data will then be analyzed using thematic analysis to unearth themes salient in the group interviews. We will structure and depict these themes using thematic networks as described by (Attride-Stirling, 2001). The software for this analysis is NVivo.

Randomized Controlled Trial Data Analysis:

We aim to identify the intention-to-treat effect of incentives on the proportion of early PNC referrals of TBA delivery clients.

$$y_{ij} = \beta_0 + \beta_1 * T_j + X_{ij} + \varepsilon_{ij}$$

Where:

- $y_{ij}$  is the total proportion of referrals for TBA  $i$ , and village  $j$  of all her delivery clients;
- $T$  is a dummy variable indicating if the TBA is in the treatment arm;
- $X_{ij}$  is a set of baseline individual-level covariates;
- $\beta_1$  is the coefficient of interest and gives the average mean difference between the treatment and the control arms.

We will also identify interactions between incentives and baseline TBA characteristics (considered proxies for social preferences) in order to clarify pathways through which the intervention might have worked. I will specify a series of equations:

$$y_{ij} = \beta_0 + \beta_1 * T_j + \beta_2 * T_j * Var_{ij} + Var_{ij} + X_{ij} + \varepsilon_{ij}$$

Where:

- $Var_{ij}$  is a binary baseline characteristic for TBA  $i$  in village  $j$  previously included in  $X_{ij}$ ;
- $\beta_1$  is interpreted as the treatment effect when  $Var_{ij} = 0$ ;
- $\beta_2$  is the additional effect of  $Var_{ij}$

**5.2. Is there a sample size/power calculation?**

No  Yes: If yes; describe the calculation and the scientific rationale, and, if applicable, by site and key characteristics such as participant demographics

Qualitative Study Sample Size

The qualitative study does not require power calculations. However, the recommended size for focus group discussions is 6-12 participants (Kielman, Cataldo, & Seeley, 2012). We will thus recruit 10 participants in each group and aim to have at least 6 attendees in each group.

### Randomized Controlled Trial Sample Size

Power calculations for this study are based on a comparison of proportion of TBA referrals for early PNC between 2 equal-sized arms for  $H_0=0$  against alternative that it is not. Qualitative evidence of a similar intervention in Nigeria was associated with an average of 5 facility referrals per recruited TBA per month (Akpan & Lah, 2012). The crude birth rate in Ebonyi State is approximately 42 births per 1000 population annually (NPC and ICF International, 2014). If 70 percent of mothers deliver at home, then TBAs can potentially deliver up to 29 births per 1000 population in a year. Thus, a total of 68092 births in Ebonyi State are eligible for referrals in a year, given the state population of 2.4 million (FMOH, 2011). There is an average of 3 TBAs per village and 30 villages per LGA. Thus approximately 90 TBAs work in each of the 13 LGAs in Ebonyi state (1170 TBAs in total). At an average of 60 deliveries per year (68092/1170), there are approximately 5 deliveries per month to each TBA. We have powered the study to detect a difference in proportion of referrals of 0.20, that is 1 extra referral/TBA/month given 5 deliveries. Assuming standard deviation in proportion of referrals equivalent to study by (Rai, 2014) of 0.37 and alpha of 0.05, a minimum sample size of 160 TBAs can detect this effect at the 5 percent level with 90 percent power. With 200 TBAs, we can detect this effect size with over 90 percent power at the 5 percent level. Given an average of 5 TBA delivery clients per month and 5-month intervention period, we expect to enroll at the minimum 4000 TBA clients. With 200 TBAs, we may enroll up to 5000 TBA clients.

The randomized controlled trial study procedures, analysis, and other aspects of the protocol will be registered with the American Economic Association's Registry for randomized controlled trials (<https://www.socialscienceregistry.org/>) prior to baseline data collection.

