##### 4.3. Indicate the total number of participants (if applicable, distinguish between the number of participants who are expected to be screened and enrolled, and the number of enrolled participants needed)

The qualitative study will recruit up to 10 TBA delivery clients, health workers, and traditional birth attendants each, aiming for a minimum of 6 participants in each category who consent and join the focus group discussions.

The randomized controlled trial will screen 200 traditional birth attendants in all and requires a minimum of 160 TBAs to consent and enroll into the study as justified in the power calculations below. The total TBA enrollment for the study will not exceed 200. We expect that TBAs will deliver an average of 5 clients per month. We intend to survey each of these clients. Thus, over the 5-month intervention period, the randomized controlled trial team will approach up to 5000 TBA delivery clients (200 \*5\*5).

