**9.5. Is a waiver or alteration of consent (and/or parental permission) being requested?**

No  Yes: **If yes; describe the rationale for the request. If the alteration is because of deception or incomplete disclosure, explain whether and how participants will be debriefed (include any debriefing materials with the application)**

Randomized Controlled Trial

The consent form for the TBAs will not include information on the referral incentive intervention. The intervention offers TBAs in the referral incentive arm an incentive for referring mothers to postnatal care in facilities. Informing TBAs in the control arm about this incentive during informed consent at baseline will have negative consequences, and the research cannot be practicably carried out without this alteration. TBAs in the control arm receive information on the need for postnatal care and an incentive for reporting each client they deliver (TBAs in the referral incentive arm receive what the control arm receives in addition). We will be unable to measure the pure effect of incentives and will instead capture the effect of receipt of incentives by referral incentive TBAs and anger or collusion by control TBAs in response to exclusion from receiving the referral incentive. We can thus not answer the research question intended. The information that will be elicited during the randomized controlled trial do not constitute more than minimal risk to subjects. This information is common knowledge in the community including TBA service patterns, demographic information, delivery client base etc.

Debriefing

All TBAs will be provided with additional information on the intervention when all follow-up survey data has been collected using the attached debriefing script. Each TBA will be approached in her home (which often doubles as the work place) within the community by one of the field enumerators. We will provide information on the incentive used in the study, the probability of selection into each study arm, and the opportunity to drop out of the study if so desired.

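### Is the floor of 160 TBAs wrong because the stated inputs give only 144 to 146?

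*Protocol*

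**What the plan says.** The power calculation in Protocol section 5.2 (Randomized Controlled Trial Sample Size) compares the TBA-level proportion of early postnatal referrals between two equal arms against a two-sided alternative. It uses a difference of 0.20, a standard deviation of 0.37 taken from another study, and alpha 0.05. It concludes that "a minimum sample size of 160 TBAs can detect this effect at the 5 percent level with 90 percent power", and that 200 TBAs would give more than 90 percent.

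Section 4.3 carries the figure into recruitment: 200 TBAs are screened, the trial "requires a minimum of 160 TBAs to consent and enroll into the study as justified in the power calculations below", and enrolment is capped at 200.

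Neither section gives a loss rate, an intracluster correlation or any other inflation factor. Drop-out is mentioned elsewhere, without a rate. Section 14.1 says "we will allow both the TBA and her clients to opt out of the study at any point" and regards this as harmless "As long as drop-out of the study is non-differential across arms and is not in high proportions". The debriefing text in section 9.5 tells TBAs about "the probability of selection into each study arm, and the opportunity to drop out of the study if so desired".

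On clients, section 5.2 says "we expect to enroll at the minimum 4000 TBA clients" with 160 TBAs. Section 4.3 says that "the randomized controlled trial team will approach up to 5000 TBA delivery clients" with 200.

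**The concern.** A reader who puts the stated inputs into the usual formula does not get 160. Section 4.3 says the power calculation justifies 160, yet the calculation yields a number 14 to 16 lower and nothing on the page bridges the gap. That raises the question of whether an input is misreported or an inflation step was left out.

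The explanation could matter because the protocol expects that TBAs may leave. If the extra TBAs are there to cover drop-out, one would like to know how much they cover. If they are there for another reason, drop-out may not be covered at all.

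The client figure invites a similar query. It is offered as a minimum, but it is the product of an average delivery rate and complete reporting, contact and consent.

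**Working it through.** **Inputs** (Protocol 5.2): difference 0.20; SD 0.37; two-sided alpha 0.05, so z = 1.960; power 90 percent, so z = 1.2816; two equal arms. Section 4.6 randomizes each TBA individually with 50-50 probability.

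**Attempt to reproduce 160.** For a two-sample comparison of means,

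n per arm = 2 × (1.960 + 1.2816)² × 0.37² / 0.20² = 71.92, rounded up to 72, or 144 in total.

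With the noncentral t distribution, 144 gives 89.6 percent and 146 gives 90.04 percent, so the solved minimum is 146. The figure of 160 is not reproduced as a minimum.

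**Power at the numbers the protocol uses.** The standardized difference is 0.20 / (0.37 × √(2/n per arm)).

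| Total TBAs | Standardized difference | Power, normal | Power, t |
|---|---|---|---|
| 144 | 3.243 | 90.0% | 89.6% |
| 146 | 3.266 | 90.4% | 90.0% |
| 160 | 3.419 | 92.8% | 92.5% |
| 200 | 3.822 | 96.9% | 96.7% |

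Both power statements in section 5.2 are therefore true: 160 reaches 90 percent, and 200 exceeds it.

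**What the margin absorbs.** From 160, 90 percent power survives a loss of 160 − 146 = 14 TBAs (14/160 = 8.75 percent, t) or 160 − 144 = 16 TBAs (16/160 = 10 percent, normal). In the other direction, 144/0.90 = 160 exactly, so an unstated 10 percent loss allowance would explain the number. That is an inference; the documents do not say it.

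Loss rates are not given, so the following are assumed, starting from 160:

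| Assumed loss | TBAs left | Power (t to normal) |
|---|---|---|
| 5% | 152 | 91.2 to 91.5% |
| 15% | 136 | 87.9 to 88.3% |
| 20% | 128 | 85.9 to 86.4% |

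**Could the margin be for village clustering?** A design effect of about 1.10 to 1.11 would also take 144 to 146 up to about 160. That inflation belongs to designs that randomize whole villages. When each TBA is randomized separately, two TBAs in one village are as likely to be in opposite arms as in the same arm, so shared village variation does not on average inflate the variance of the arm difference. Simulating 53 villages of 3 TBAs (159 in all) with total SD 0.37, difference 0.20 and 20,000 runs per setting gave 92 to 93 percent power at village correlations of 0, 0.05 and 0.20. Clustering therefore neither explains the margin nor uses it up.

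**Clients.** The protocol's wording is "At an average of 60 deliveries per year (68092/1170"), which is 58.2 a year or 4.85 a month, rounded there to about 5.

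- 160 TBAs × 5 months × 5 a month = 4000.
- 160 TBAs × 5 months × 4.85 a month = 3880.
- The gap is 120/4000 = 3 percent.
- If 90 percent of clients were reported, reached and consenting (an assumed rate), the range would be 3492 to 3600.

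None of these figures enters the TBA-level power calculation.

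**The case for a change.** The strongest case for a change is that a power calculation should be reproducible. Section 4.3 says outright that 160 is justified by the calculation, and it is not the number the calculation returns. The screening step from 200 to 160 does not fill the gap, because it concerns consent before enrolment. One sentence naming the margin would cost nothing, and it would put a number on the drop-out that section 14.1 leaves as not high.

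The arithmetic in that case is right, and the margin is indeed unexplained. The inference to an error fails. It requires the word minimum to mean the smallest solution of the formula, whereas section 4.3 uses it for the fewest TBAs who must enrol. On that reading the claim of 90 percent power is met with some to spare.

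Section 14.1 is also weak support. It is a privacy provision covering TBAs and clients together, and it concerns the ability to estimate effects; it makes no promise about power. The debriefing exit in section 9.5 comes after follow-up data are complete, and no rate is attached to it.

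Quoting 92.5 percent instead would not clearly be better. It would rest on a standard deviation borrowed from another study and on an unadjusted t-test, while the planned analysis is a regression with baseline covariates.

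On clients, the wording is loose, since women may decline. But the sentence is already conditioned on the average of 5 deliveries a month, and 4000 marks the 160-TBA case against 5000 for 200.

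**Conclusion.** No change to the plan is needed. The stated inputs give 144 to 146 TBAs and the protocol sets its floor at 160, which is 14 to 16 higher and in the conservative direction. Following the plan as written yields 92.5 to 92.8 percent power at the floor and 96.7 to 96.9 percent at the cap. What is missing is a reason for a safe margin, and supplying one would leave enrolment, design and analysis as they are. The client count is an expectation worded as a minimum, 3 percent above the protocol's own unrounded rate before any refusals, and nothing in the power calculation depends on it.

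This rests on the SD of 0.37 holding, on TBAs being randomized individually as section 4.6 describes, and on TBA loss staying within about 9 to 10 percent. Beyond that, power falls gradually, to about 88 percent at an assumed 15 percent loss from 160. The treatment indicator in section 5.1 carries a village subscript, but the SAP's version of the model does not, and the procedures assign each TBA separately.
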